Patients who met the inclusion and exclusion criteria were randomly assigned to either the RDI group or the conventional white-light endoscopy (WLE) group. In the RDI group, the submucosal dissection was performed entirely under RDI mode (white-light mode was allowed only for observation and marking). In the WLE group, the entire ESD procedure was completed with white-light mode without switching to RDI. All ESD procedures were performed by experienced endoscopists (≥ 300 previous ESD cases and formal RDI training, with ≥ 20 ESD cases performed under RDI mode).

Outcome parameters

The primary outcome parameter is the mean resection speed (mm^2/min) achieved with RDI versus conventional WLE during ESD.

The secondary outcome parameters are: complete resection (R0) rate, en-bloc resection rate, resection margin, number of intra-procedural bleeding episodes, intra-procedural blood loss, intra-procedural hemostasis time, other intra-procedural adverse events, and post-procedural adverse events.

The results will be analyzed in full analysis set, per-protocol set and safety set.

After the overall analysis, all data will be stratified by lesion location and analyzed separately for esophageal, gastric, and colorectal subgroups.

Definitions

The mean resection speed is the result of resection area divided by the resection time. The resection area is defined as the area on the specimen-fixation board. The resection time is defined as the time from the first mucosal incision to complete dissection of the lesion. Adverse events included bleeding, perforation, infection, and so on, mentioned by Cotton et al. (Gastrointest Endosc. 1994;40:514-518).

Sample Size

Based on a pilot study of 20 cases at our center, the mean resection speed in the RDI group was $27.2 \pm 9.8 \text{ mm}^2/\text{min}$ versus $21.1 \pm 12.2 \text{ mm}^2/\text{min}$ in the white-light group.

Assuming H_0 : no difference in mean resection speed between the two groups, and setting $\alpha = 0.05$ and power = 0.90, the required sample size is 71 lesions per arm (142 total).

Allowing for a 10 % dropout rate, we plan to enroll 79 lesions per arm, yielding 158 lesions in total (each lesion requiring ESD is counted as one case, even if multiple lesions occur in the same patient).

Randomization

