Stratified randomization by center. Random numbers generated in Excel by an independent statistician; sequentially numbered, sealed, opaque envelopes prepared and held by the third party. The envelopes constitute the allocation sequence; random numbers remain concealed from patients and endoscopists until the envelope is opened immediately before allocation.

Blinding

Patients will be blinded; operators and video reviewers cannot be blinded; pathologists will remain blinded.

Statistical analysis

All analyses were performed with SPSS version 26. Baseline characteristics were examined to assess balance across concentration groups. Normally distributed continuous variables are presented as mean \pm SD and compared between groups using independent-samples t-tests; non-normally distributed continuous variables are expressed as median (interquartile range) and compared with the Wilcoxon rank-sum test. Categorical rates were compared using the χ^2 test. A two-sided $P < 0.05$ was considered statistically significant.

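### Does naming only the chi-square test for categorical outcomes make sparse adverse-event and resection tables falsely significant?

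*Protocol*

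**What the plan says.** The Statistical analysis section of the protocol covers all proportions in one sentence ("Categorical rates were compared using the" chi-square test), and sets the level with "A two-sided $P < 0.05$ was considered statistically significant". It does not mention an exact test, a continuity correction or a rule for small expected counts.

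The outcomes concerned are secondary. The Outcome parameters section lists "complete resection (R0) rate, en-bloc resection rate" and intra- and post-procedural adverse events. The Definitions section describes the last of these as "Adverse events included bleeding, perforation, infection, and so on". All data are also to be analysed separately by esophageal, gastric and colorectal location. The protocol gives no expected rate for any categorical outcome and no subgroup sizes.

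The primary outcome, mean resection speed, is continuous, and the sample size rests on it alone.

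**The concern.** The chi-square P value is a large-sample approximation, and a common rule of thumb asks for expected counts of at least 5. With 79 lesions per arm that needs a pooled rate of at least 5/79 = 6.3%. If the three locations were equally frequent, each would have about 26 lesions per arm and the threshold would be 5/26 = 19.2%. Perforation, infection or failed en-bloc resection could well be rarer than that. The same section gives continuous variables a fallback when normality fails, so the lack of one for proportions stands out.

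If the approximation failed badly in the anti-conservative direction, a handful of events could be reported as a significant safety difference for or against RDI. In a trial whose title promises a safety comparison, that would matter.

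**Working it through.** **Inputs.** From the protocol: 79 lesions per arm enrolled, 71 evaluable, two-sided 5% level. Assumed, because the protocol is silent: event or failure rates of 1% to 20%, and equal-thirds subgroups of about 26 per arm. Success and failure are interchangeable in a 2×2 table, so a 95% en-bloc rate behaves like a 5% event rate.

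**The plan's own figure.** The pilot inputs are "the mean resection speed in the RDI group was $27.2 \pm 9.8" against 21.1 ± 12.2 mm²/min.
- Difference: 27.2 − 21.1 = 6.1. Mean variance: (9.8² + 12.2²)/2 = 122.44, so the SD is 11.07.
- Normal approximation: 2 × (1.960 + 1.282)² × 122.44 / 6.1² = 69.2, so 70 per arm. The t-based solution is 70.12, rounded up to 71.
- Dropout: 71/0.90 = 78.9, so 79 per arm and 158 in total.

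This reproduces "and power = 0.90, the required sample size is 71 lesions per arm (142 total" and the enrolment target. It involves no categorical test.

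**One table by hand: 4 v 0 at 79 per arm.**
- Uncorrected chi-square: 158 × (4 × 79)² / (79 × 79 × 4 × 154) = 4.10, P=0.043.
- With continuity correction: 158 × (4 × 79 − 79)² / (79 × 79 × 4 × 154) = 2.31, P=0.129.
- Fisher: 2 × (79·78·77·76)/(158·157·156·155) = 0.120. The mid-P version halves the probability of the observed split and of its mirror image: 0.060.

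The tables that raise the concern, done the same way:

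| Lesions per arm | Split | Uncorrected | Corrected | Fisher | Mid-P |
|---|---|---|---|---|---|
| 79 | 4 v 0 | 0.043 | 0.129 | 0.120 | 0.060 |
| 79 | 5 v 0 | 0.023 | 0.069 | 0.059 | 0.029 |
| 79 | 7 v 1 | 0.030 | 0.070 | 0.063 | 0.035 |
| 26 | 4 v 0 | 0.037 | 0.119 | 0.110 | 0.055 |
| 26 | 6 v 1 | 0.042 | 0.104 | 0.099 | 0.055 |

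**False-positive rate of the rule.** For a common true rate p, add Bin(a; n, p) × Bin(b; n, p) over every pair (a, b) whose P value is below 0.05:

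| True rate | Uncorrected, 79 per arm | Fisher, 79 per arm | Uncorrected, 26 per arm | Fisher, 26 per arm |
|---|---|---|---|---|
| 1% | 0.8% | 0.01% | 0.02% | <0.01% |
| 2% | 3.1% | 0.2% | 0.2% | <0.01% |
| 3% | 4.4% | 0.7% | 0.7% | 0.01% |
| 5% | 5.0% | 1.6% | 2.2% | 0.1% |
| 10% | 5.2% | 2.8% | 5.0% | 1.0% |
| 20% | 5.2% | 3.2% | 5.6% | 2.3% |

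The maximum at 79 per arm is 5.3%, at a rate of 7.4%. Restricted to rates with an expected count below 5, the maximum is 5.2% at 79 per arm, 5.2% at 71 and 5.6% at 26. Unequal subgroup arms of 18/34 and 20/32 peak at 5.4% and 5.3%.

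**Why one table misleads.** Given exactly 4 events in total, a 4–0 split has probability 12.0% under no difference. But at a 2% rate a total of 4 occurs with probability C(158,4) × 0.02⁴ × 0.98¹⁵⁴ = 17.8%, so this route contributes 0.178 × 0.120 = 2.1%. A total of 3 or fewer occurs 61.1% of the time (the binomial sum over 0 to 3), and the test then cannot reject, since even 3 v 0 gives P=0.080. The 12% comes from picking one event total.

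**What Fisher would cost.** Summing in the same way with true rates of 1% and 8% at 79 per arm gives power of 61% for uncorrected chi-square, 54% for mid-P and 40% for Fisher.

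**The case for a change.** The strongest case is that the protocol is not silent: it prescribes a test for every categorical rate, and a reader meets one table, not an average over all possible ones. Someone shown 4 v 0 perforations with P=0.04 would take that as stronger evidence than the conditional 12% supports. In addition, the sentence does not fix whether a continuity correction applies, and at 4 v 0 that choice moves P from 0.043 to 0.129.

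Some of this stands. The P values are right, expected counts below 5 are plausible (above all in subgroups), and a written small-cell rule would be tidier.

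It does not make the stated test wrong. Conditioning on the event total is one defensible view of a 2×2 table, but a test is planned before that total is known, and the error rate that counts at planning is the unconditional one. The open continuity correction also cuts the other way: the wording permits it, and with it none of the five tables is significant. Mid-P, the usual remedy for Fisher's conservatism, agrees with uncorrected chi-square that 5 v 0 and 7 v 1 at 79 per arm are significant. Experienced statisticians differ over these tests, and for safety outcomes Fisher's loss of power is a real cost.

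**Conclusion.** The concern does not hold. With equal arms the prescribed test keeps its false-positive rate between 0.8% and 5.3% at 79 lesions per arm for event rates of 1% to 10%, and at or below 5.6% at 26 per arm for rates up to 20%. For truly rare events it falls below the nominal 5%. That expected counts will be below 5 cannot be shown from the protocol, which gives neither event rates nor subgroup sizes.

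These results assume independent lesions, the event rates stated above and subgroups of roughly a third of the sample. A much smaller subgroup of 13 per arm could reach 6.8% with an expected count below 5, but only at a rate near 38%, which is not a rare event. For rates of 1% to 20% it stays at or below 4.3%.

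The primary outcome and the sample size are untouched, and no decision rule is attached to the categorical comparisons. A fallback for sparse tables, and the form of any confidence intervals, are details commonly left to the statistical analysis plan. Their absence from this protocol is not an error.
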